CRF	Case Report Form
DSMB	Data and Safety Monitoring Board
FDA	Food and Drug Administration
GCP	Good Clinical Practice
HIPAA	Health Insurance Portability and Accountability Act
IB	Investigator's Brochure
IRB	Institutional Review Board
MNX	Minoxidil
PHI	Protected Health Information
PI	Principal Investigator
PRP	Platelet Rich Plasma
SAE	Serious Adverse Event/Serious Adverse Experience
SOP	Standard Operating Procedure

Study Summary

Title	Minoxidil Foam compared to PRP for Androgenic Alopecia in Women, A Randomized Controlled Pilot Trial
Running Title	PRP for Hair loss in Women
Protocol Number	1
Phase	Pilot
Methodology	Randomized, Controlled, Crossover
Overall Study Duration	12 Months
Subject Participation Duration	12 months
Single or Multi-Site	Single Site
Objectives	Determination of non-inferiority treatment of PRP compared to standard of care MNX in women
Number of Subjects	23
Diagnosis and Main Inclusion Criteria	Female, 18 years or older, Androgenic Alopecia grade I-II by Ludwig classification
Study Product, Dose, Route, Regimen	Platelet Rich Plasma 10cc, Injection by Nappage technique, 3 injections - 1 time every 4 weeks for 3 months
Duration of Administration	12 Weeks (1 time every 4 weeks for 3 months)
Reference therapy	Minoxidil
Statistical Methodology	Wilcoxon signed rank test for comparison of outcomes between treatments and McNemar's exact test for categorical outcome variables

1 Introduction

This document is a protocol for a human research study. This study will be carried out in accordance with the applicable United States government regulations and Mayo Clinic research policies and procedures.

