7.2 Statistical Methods

Data Analysis – Given the design, all statistical analysis will be focused on the difference in outcomes, and differences in outcomes compared to baseline, for each treatment within individual patients. For continuous or ordinal outcome variables, we will use a Wilcoxon signed rank test for comparison of outcomes between PRP and Minoxidil, while for categorical outcome variables we will use McNemar's exact test for these. Continuous outcome measures will be summarized using the sample mean, standard deviation, median, minimum, 25th and 75th percentiles, and maximum. Categorical variables will be summarized with number and percentage. 95% confidence intervals (CIs) will be estimated where appropriate. P-values of 0.05 or less will be considered as statistically significant, however the results of these tests will be interpreted with the low power of this pilot study in mind; more emphasis will be placed on graphical and descriptive summaries than on the results of statistical tests. No adjustment for multiple testing will be made owing to the exploratory, pilot nature of the study. Given the prospective nature of the study, we expect to encounter little if any missing data. However in the event of missing data, no attempt to impute this missing data will be made in this pilot study; missing data will be treated as missing.

Descriptive Statistics

We will summarize continuous variables using the sample mean, standard deviation, median, minimum, 25th and 75th percentiles, and maximum. We will summarize categorical variables with number and percentages. Ordinal variables will be summarized using the sample median, minimum, 25th and 75th percentiles, and maximum, as well as with number and percentage.

Handling of Missing Data

Given the prospective nature of the study, we expect to encounter little if any missing data. However in the event of missing data, no attempt to impute this missing data will be made in this pilot study; missing data will be treated as missing.

Multiplicity

No adjustment for multiple testing will be made owing to the exploratory, pilot nature of the study. P-value of 0.05 or less will be considered as statistically significant.

Primary Hypothesis:

We hypothesize that PRP administration for AGA will be safe and without significant complications for the patient. AGA will be comparable in efficacy or superior to conventional treatment with MNX.

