The primary endpoints of the study, occurrence of adverse reactions and morbidity, are both dichotomous categorical variables. As such, the proportion for which these outcomes occur will be estimated along with 95% CIs. These proportions will be compared between treatments using McNemar's exact test

Interim Analysis

No interim analysis will be performed in this pilot study.

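### The stated objective is non-inferiority of PRP to minoxidil, but the plan has no margin or confidence-bound rule, and its two lists of primary endpoints disagree on hair growth

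*Combined protocol and SAP*

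**What the plan says.** The Study Summary has a single entry under Objectives: "Determination of non-inferiority treatment of PRP compared to standard of care MNX in women". Its Statistical Methodology entry names a "Wilcoxon signed rank test for comparison of outcomes between treatments" and McNemar's exact test for categorical outcomes. Section 7.2 repeats this for continuous or ordinal outcomes: "we will use a Wilcoxon signed rank test for comparison of outcomes between PRP and Minoxidil". Significance is set at a p-value of 0.05 or less, with no statement of one- or two-sided testing.

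The efficacy half of the primary hypothesis in Section 7.2 reads "AGA will be comparable in efficacy or superior to conventional treatment with MNX". The subject of that sentence is the disease; PRP appears to be meant. Section 1.1 puts the same idea as similar or better hair growth.

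Other parts describe a more modest study. Section 2 gives the primary objective as a pilot study of PRP efficacy and does not mention non-inferiority. Section 7.1 reports that no power calculation was done and that the data are meant to help design a larger trial. Section 7.2 adds that "the results of these tests will be interpreted with the low power of this pilot study in mind", that "more emphasis will be placed on graphical and descriptive summaries than on the results of statistical tests", and that "95% confidence intervals (CIs) will be estimated where appropriate".

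On endpoints, Section 3.2 lists two primary endpoints: hair growth under each treatment, and morbidity from PRP administration. Section 7.2 states: "The primary endpoints of the study, occurrence of adverse reactions and morbidity, are both dichotomous categorical variables".

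**The concern.** A non-inferiority conclusion needs a stated margin and a rule, usually that the confidence bound unfavourable to the new treatment lies inside it. Neither is given. The tests that are named take no difference as their null hypothesis, so they can reject equality but cannot show that PRP is not materially worse. The trial could finish with clean data and no agreed way to say whether its objective was met. Because the hypothesis is worded as comparability, a p-value above 0.05 would be an easy but invalid substitute.

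The endpoint conflict adds to this. The objective concerns efficacy, yet the section that governs the analysis leaves the efficacy outcome off its list of primary endpoints. A reader of the results could not tell whether the hair-growth comparison was a primary finding.

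**Working it through.** **1. What each possible result would settle for one hair-growth outcome**

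| Result of the named test | What the plan lets one conclude about non-inferiority |
|---|---|
| Significant, favours PRP | Superiority, which implies non-inferiority on that outcome |
| Not significant | Nothing defined |
| Significant, favours minoxidil | PRP is worse, but with no margin the plan does not say whether by too much |

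**2. Is there a figure to reproduce?** No. The sample size of 23 comes without a margin, SD, effect size or power (Section 7.1), so it can be neither reproduced nor called wrong.

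**3. The test at n = 23.** Inputs: 23 patients (Section 7.1), significance at 0.05 (Section 7.2). Assumptions: 23 complete pairs, no ties, no period or carryover effect, two-sided testing. The rank sum runs from 0 to 23 × 24 / 2 = 276. Under equality the exact lower-tail probability at 73 is 203,176 / 8,388,608 = 0.0242, so the two-sided size is 2 × 0.0242 = 0.048. A cut-off of 74 would give 0.0522, above 0.05. The critical value is therefore 73.

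**4. How often is the test non-significant when PRP is truly worse?** Further assumption: within-patient differences (PRP minus minoxidil) are normal with SD 1, so effects are in units of that SD, which the documents do not give. With mean difference −d, 200,000 simulated trials at each d and the critical value of 73:

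| PRP truly worse by | Proportion non-significant |
|---|---|
| 0.3 SD | about 0.73 |
| 0.5 SD | about 0.39 |

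Fewer complete pairs would raise both.

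**5. What 23 pairs could support.** With true difference zero and one-sided 0.025, the paired normal formula gives the margin for 80% power as (1.960 + 0.842) / √23 = 2.802 / 4.796 = 0.58 SD. The noncentral t gives 0.61 SD. Simulation using the Hodges-Lehmann interval, the one that matches the signed rank test, gives about 0.63 SD. That interval has a mean half-width of about 0.44 SD. These figures are for illustration; the point does not depend on them.

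**6. The two endpoint lists side by side**

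| | Section 3.2 | Section 7.2 |
|---|---|---|
| Hair growth | Primary | Not listed |
| Morbidity | Primary | Primary |
| Adverse reactions | Not listed as such | Primary |

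Section 7.2 describes its primary endpoints as dichotomous. Hair density by phototrichogram (Sections 3.1 and 6) is not dichotomous, so hair growth measured that way cannot be read into that list.

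**The case against.** The strongest reply is that this is openly a pilot. Non-inferiority appears once, in a summary line. Section 2 states the objective without it, Section 7.1 disclaims power, and Section 7.2 puts description ahead of testing, warns about low power and allows for confidence intervals. On that view the body is already close to an estimation study and only the label is wrong. Much of this stands, and it lowers the seriousness. It does not remove the mismatch: the primary hypothesis repeats the comparability claim, and none of these passages says what would count as meeting the objective.

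Four stronger readings are tempting and should not be drawn.

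- A reader might infer that the sponsor intends to report p above 0.05 as comparability. No passage says so, and the low-power caveat partly guards against it.
- A reader might cite the chance of a significant result favouring PRP when the treatments are equal, about 2.4%, as a defect of this design. That is simply one side of the test's size. It assumes two-sided testing; one-sided at 0.05 the exact figure is 4.9% (critical value 83).
- A reader might infer that hair growth goes unanalysed. It does not: the general Wilcoxon plan in Section 7.2 covers it. Only its primary status is contradictory.
- A reader might infer that 23 patients is an error. The documents make no power claim for that number.

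**Conclusion.** The point holds as something that should be fixed, because the plan is wrong as written. Its stated objective is non-inferiority, and its named analyses cannot deliver that conclusion except through a superiority finding. A non-significant result is no substitute: it occurs in about 73% of trials if PRP is worse by 0.3 SD and about 39% if worse by 0.5 SD. These sizes rest on 23 complete pairs, two-sided 0.05, normal differences, no period or carryover effect, and an SD scale that the documents do not supply. The absence of a margin and bound rule needs no calculation.

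The conflict between Sections 3.2 and 7.2 over hair growth is a separate contradiction, and it is certain on the text. The pilot purpose and descriptive emphasis keep both matters below the level of a fatal flaw.

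**What to change.** **Objective and hypothesis.** Replace the Study Summary objective and the efficacy sentence of the primary hypothesis with an estimation aim that agrees with Sections 2 and 7.1. Suggested text: *To estimate the within-patient PRP minus minoxidil difference in hair growth, with a two-sided 95% confidence interval, to inform the design of a later trial. A p-value above 0.05 will not be reported as comparability or non-inferiority.* The Hodges-Lehmann estimate and interval suit the planned Wilcoxon test, though other paired intervals would serve. The new wording also removes the slip in the hypothesis sentence; align Section 1.1 with it.

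**Define the difference.** Use visits already scheduled at the end of each treatment period, months 3 and 8. State whether change in the second period is measured from enrolment or from month 5, since the protocol uses the word baseline only for the enrolment visit.

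**If non-inferiority is kept.** Pre-specify a justified margin and a confidence-bound rule before any data are seen.

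**Endpoints.** Reconcile Sections 3.2 and 7.2 into one list; the sponsor must decide which is intended. If hair growth stays primary, name one measure already collected, such as phototrichogram hair density. The existing safety analysis text can remain.

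**Cost.** An amendment submitted to the IRB (Section 11) and a more modest stated claim. Phototrichograms are already scheduled at baseline and months 3, 5, 8 and 12, so no visits, procedures or patients are added.

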1.1 Background

Androgenic alopecia (AGA) is a common, progressive hair loss disorder affecting both sexes with significant negative impact on social and psychological well-being. The frequency and severity increases with age, and up to 80% of men, and 50% of women are affected by AGA over the course of their lives. (Piraccini 2014) (Varothai) (Bologna - book) While men are more frequently affected, the psychological impact is likely to be high for women where the social impact of hair loss is often devastating. Current medical therapies specifically approved by the US FDA are limited to minoxidil (for men and women) and finasteride (for men only) (Varothai), but variable responses and the need for indefinite use often result in patient fatigue and suboptimal compliance. (Gupta)

Recently, there has been interest in treatments orientated to more biologically regenerative therapies, and consequently there have been numerous studies that have demonstrated successful use for platelet rich plasma (PRP) in treating AGA. (Singhal) (Maria-Angeliki) (Gentile) (Trink) (Gkini) (Cerveli) (Uebel) (Greco) (Takikawa) (Kang) (Betsi) (Sclafani) (Khatu) (Schiavone) PRP contains concentrated platelet cells derived from autologous whole blood that are believed to activate a cascade of growth factors when injected into an area of poor hair growth that stimulates hair growth. (Jain)(Lubkowska) In this proposal we will examine whether PRP therapy provides similar or better hair growing capacity in women compared to the conventional topical application minoxidil.

1.2 Investigational Agent

Platelet Rich Plasma (PRP)

1.3 Clinical Data to Date

PRP is an autologous concentration of human platelets in a small volume of plasma that has a 4-7 times higher platelet concentration than baseline.(Jain) (Lubkowska) (Parsley) Since activated platelets secrete a number of cytokines and growth factors, such as platelet-derived growth factor, epidermal growth factor, transforming growth factor, and vascular endothelial growth factor, (Jain) (Lubkowska) (Parsley) PRP may provide an attractive therapy to promote hair growth in the declining hair follicle.

Recent investigators have explored the use of PRP as a treatment modality for AGA, with most available studies to date showing positive results. (Singhal) (Maria-Angeliki) (Gentile) (Trink) (Gkini) (Cerveli) PRP is attractive as a useful treatment for nonscarring alopecia's such as AGA, because the treatment is safe and adverse effects appear to be negligible. (Singhal) (Maria-Angeliki) (Gentile) (Trink) (Gkini) (Cerveli) However, the effect of PRP on hair growth has been studied primarily in men. Studies that include men and women usually do not analyze the data according to sex or comment on whether sex differences were observed. (Trink) (Takikawa) (Kang) (Betsi) (Sclafani) (Schiavone) (Gkini) Although sex differences are known to exist in the incidence, diagnosis and mechanisms leading to AGA, women are understudied (Farage) (Romanelli). The need to understand hair loss in women is underscored by the growing interest of cosmetic dermatologists and plastic surgeons to use PRP routinely in their aesthetic and rejuvenation practice to reduce/prevent hair loss.

A recent review of the available literature regarding PRP treatment for hair loss identified 14 articles describing the use of PRP, 12 of which were used for AGA. (Maria-Angeliki) This systematic review considered 7 studies to be of moderate quality, 4 of low quality and 3 of very low. Of the 7 trials of moderate quality, all reported a statistically significant increase in the number of hairs and hair density following PRP therapy, indicating a positive response to treatment. The predominant criticisms of the trials to date are the lack of a consensus protocol regarding the exact concentration of PRP, dose, frequency, depth of injections, and number of required sessions. Variability in evaluation methods also limits accurate comparison between the studies (i.e., global photographs, phototrichograms, dermoscopic images, hair pull test, and manual counting were all reported as measurement tools). In addition, these studies predominantly used men. Very little published data exists for PRP use in women with AGA. The studies that did include women examined very low numbers and/or did not analyze results according to sex so that it is not possible to evaluate whether PRP therapy is safe and efficacious in women. (Trink) (Takikawa) (Kang) (Betsi) (Sclafani) (Schiavone) (Gkini) Nonetheless, PRP appears to be a useful treatment for AGA, particularly in men, and there is an urgent need for randomized controlled studies with standardized measurement techniques and reproducible protocols to study clinical efficacy. Considering the widespread use of PRP in cosmetic clinics among women and the lack of data on the effect of PRP on hair regeneration in women there is a great need to perform a controlled trial in women. In future studies we would like to examine whether PRP is equally effective in men and women and to examine its mechanism of action.

1.4 Dose Rationale and Risk/Benefits

We will dose PRP in a manner similar to previous trials. (Gentile, Trink, Cerveli) Fresh PRP will be harvested from the individual and their own PRP administered at three time points, once every 4 weeks for a totally treatment time of 12 weeks. Minoxidil will be used according to FDA and manufacturer instructions daily for 12 weeks.

Risks associated with PRP therapy include possible pain, redness, and/or irritation at the site of injections for up to 2-3 days post injection. Published human data indicate no significant adverse events related to injection of PRP into the skin and previous authors utilizing similar protocols reported no infection, fever, hematoma, tissue hypertrophy, or major adverse events among the subjects. (Singhal) (Cerveli) (Gentile) (Trink) (Gkini) Known possible risks for Minoxidil include chest pain, rapid heartbeat, faintness, dizziness, sudden or unexplained weight gain, swelling of the hands or feet, scalp irritation or redness, changes in hair color and texture, and unwanted facial hair growth.

[figure not shown]
2 Study Objectives

The overall goal of this study is to develop regenerative cell therapy for use in female patients with AGA. The primary objective of this proposal is to conduct a pilot study on the efficacy of using PRP to treat this type of hair loss in females.

3 Study Design

3.1 General Design

The study will be a randomized control trial following a crossover design to compare PRP to MNX in females.

Subjects will be recruited from the clinical practice of the Department of Dermatology, Mayo Clinic Florida. 23 females with AGA grades I-II based on the Ludwig Classification. (Ludwig)

Patients will be randomized into a PRP then MNX (Arm A) or MNX then PRP group (Arm B). Both treatments will be administered for 12 weeks with a 2 month washout period in between treatments. Hair density and adverse events will be assessed using Phototrichograms, Macroscopic Photos, physical exams and patient questionnaires. All patients will be followed for efficacy and adverse events at 3 month intervals until 1 year after enrollment.

3.2 Primary Study Endpoints

- 1) Hair growth related to each of the two treatment arms.
- 2) Morbidity related to PRP scalp administration.

3.3 Secondary Study Endpoints

- 1) To collect PRP samples to study the molecular mechanisms of PRP and hair growth

3.4 Primary Safety Endpoints

- 1) Documentation will include levels of pain at injection sites, any evidence of adverse reaction in the skin (e.g., swelling, erythema, warmth) and any other concerns expressed by patients.

4 Subject Selection Enrollment and Withdrawal

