5.5 Prior and Concomitant Therapy

Subjects will not be allowed any concomitant therapy for hair loss treatment.

No prior hair replacement / treatment surgeries.

No topical and systemic therapies for hair loss 3 months prior to study enrollment.

6 Study Procedures

- a.** At baseline all patients will undergo a clinical exam, assessments of hair density using phototrichograms, macroscopic photographs, patient questionnaires and labs including CBC, ferritin, thyroid function, testosterone, TSH and pregnancy test for premenopausal women. All patients will also have a small area shaved at the center of the treatment area, as well as a small tattoo injection to allow for follicle counting via the computerized software.
- b.** At 3 months, 5 months, 8 months and 12 months, patients will have repeat clinical exams and phototrichograms, macroscopic photographs and complete patient questionnaires.
- c.** At 12 months, repeat serum tests (CBC, ferritin, thyroid function, testosterone, TSH) will be performed.
- d.** Adverse events will be assessed at each visit (3, 5, 8 and 12 months post enrollment) as well as 1 week after each injection of PRP.
- e.** Shampoo and conditioner will be standardized with the study supplying Free & Clear brand products to the patients free of charge for the duration of the study.
- f.** Pre-menopausal patients will undergo a second pregnancy test before beginning the cross-over treatment.

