6.1 PRP vs Minoxidil Study Calendars

Arm A – PRP then MNX

Procedure	Baseline	Week 1	Week 4	Week 5	Week 8	Week 9	Month 3/ Week 12	Month 5/ Week 20	Month 8/ Week 32	Month 12/ Week 48
Consent	X									
Clinical Exam	X						X	X	X	X
Labs	X							X*		X
Phototrichograms & Macroscopic Photos	X						X	X	X	X
Questionnaire	X						X	X	X	X
PRP Injections	X		X		X					
Minoxidil Treatment Daily								X		
Adverse Events		X	X	X	X	X	X	X	X	X
Clinical Assessment of Injection Sites		X		X		X				
Collection of Research Samples	X		X		X					

*- pre-menopausal patients will have a second pregnancy test at the end of the washout period before beginning the cross-over treatment.

Arm B – MNX then PRP

Procedure	Baseline	Month 3/ Week 12	Month 5/ Week 20	Week 21	Week 24	Week 25	Week 28	Week 29	Month 8/ Week 32	Month 12/ Week 48
Consent	X									
Clinical Exam	X	X	X						X	X
Labs	X		X*							X
Phototrichograms & Macroscopic Photos	X	X	X						X	X
PRP Injections			X		X		X			
Minoxidil Treatment Daily	X									
Questionnaire	X	X	X						X	X
Adverse Events		X	X	X	X	X	X	X	X	X
Clinical Assessment of Injection Sites				X		X		X		
Collection of Research Samples			X		X		X			

*- pre-menopausal patients will have a second pregnancy test at the end of the washout period before beginning the cross-over treatment.

7 Statistical Plan

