7.1 Sample Size Determination

A total of 23 patients will be enrolled in this study. This sample size will be sufficient in order to gain valuable data to be used in the design of a future, larger study. Given the pilot/feasibility nature of the study, no formal power calculations were performed.

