8.2 Recording of Adverse Events

All adverse events will be documented as required under 21 CFR part 1271. Depending on the nature and seriousness of the adverse reaction, the IRB will be notified according to the Mayo Clinic IRB policy. If An SAE occurs it will also be reported to the FDA as per regulations

At each contact with the subject, the study team must seek information on adverse events by specific questioning and, as appropriate, by examination. Information on all adverse events should be recorded immediately in the source document, and also in the appropriate adverse event section of the case report form (CRF) or separate worksheet. All clearly related signs, symptoms, and abnormal diagnostic, laboratory or procedure results should recorded in the source document.

All adverse events occurring during the study period must be recorded. The clinical course of each event should be followed until resolution, stabilization, or until it has been ultimately determined that the study treatment or participation is not the probable cause. Serious adverse events that are still ongoing at the end of the study period must be followed up, to determine the final outcome.

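### Optional, low-cost improvement: every dedicated injection-site assessment falls on day 7, no contact falls on days 1-3, and no check is stated to follow the injection

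*Combined protocol and SAP*

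**What the plan says.** - **What is to be documented.** Section 3.4 lists "levels of pain at injection sites, any evidence of adverse reaction in the skin (e.g., swelling, erythema, warmth") and any other concerns that patients raise.
- **How long local reactions may last.** Section 1.4 gives the PRP risks as "possible pain, redness, and/or irritation at the site of injections for up to 2-3 days post injection".
- **When sites are examined.** In the Section 6.1 calendars the row "Clinical Assessment of Injection Sites" is marked at weeks 1, 5 and 9 in Arm A and weeks 21, 25 and 29 in Arm B. Injections are at Baseline and weeks 4 and 8 in Arm A, and at weeks 20, 24 and 28 in Arm B.
- **When adverse events are sought.** Section 6 item d has them "assessed at each visit (3, 5, 8 and 12 months post enrollment) as well as 1 week after each injection of PRP". Section 8.2 is broader: "At each contact with the subject, the study team must seek information on adverse events by specific questioning and, as appropriate, by examination".
- **How the data are used.** Section 7.2 treats the primary safety endpoints as yes/no: "occurrence of adverse reactions and morbidity, are both dichotomous categorical variables". Each proportion gets a 95% confidence interval, and "These proportions will be compared between treatments" with McNemar's exact test.
- **What the pilot is for.** Section 7.1 says that 23 patients suffice to "gain valuable data to be used in the design of a future, larger study".

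**The concern.** The signs named in Section 3.4 are of the kind that Section 1.4 says may be gone within 2-3 days, yet the one examination devoted to the injection sites comes on day 7. That timing suits reactions that outlast the stated window. It does not suit brief swelling, erythema or warmth, nor a pain level, since both would have to be recalled rather than observed.

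An injection-day check could fill the gap, but the sections differ on whether there is one, and none places it after the injection. If staff ask about adverse events before injecting, the visits at weeks 4, 8, 24 and 28 look back over the previous cycle and say nothing about the injection about to be given.

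At stake is the usefulness of the PRP tolerability figures to the larger study that this pilot is meant to inform. Brief visible signs may be under-recorded, and recalled pain may err in either direction.

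**Working it through.** **1. Timing, from the Section 6.1 calendars and Section 1.4**

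Gap = (assessment week − injection week) × 7 days.

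| Injection | Site assessment | Gap | Contacts on days 1-3 | Adverse-event check marked in injection column |
|---|---|---|---|---|
| Arm A, Baseline | week 1 | 7 days | none | no |
| Arm A, week 4 | week 5 | 7 days | none | yes |
| Arm A, week 8 | week 9 | 7 days | none | yes |
| Arm B, week 20 | week 21 | 7 days | none | yes |
| Arm B, week 24 | week 25 | 7 days | none | yes |
| Arm B, week 28 | week 29 | 7 days | none | yes |

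This reproduces the one-week interval in Section 6 item d. Set against the 2-3 day window, 7 − 3 = 4 and 7 − 2 = 5, so the assessment comes 4-5 days after the window closes. If all 23 patients receive all three injections, that applies to 23 × 3 = 69 assessments.

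**2. Injection-day checks, section against section**

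- Section 6 item d covers one of the six injection columns (Arm B, month 5).
- The calendars mark five of six, omitting Arm A Baseline.
- Section 8.2, read as every contact, covers all six.
- None of the three, nor the injection procedure in Section 5.4, states that a check follows the injection.

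**3. Scheduled adverse-event contacts, from after treatment start to the end of that 12-week period**

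- PRP: Arm A weeks 1, 4, 5, 8, 9, 12 = 6; Arm B weeks 21, 24, 25, 28, 29, 32 = 6.
- Minoxidil: Arm A week 32 = 1; Arm B week 12 = 1.

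**4. Possible effect on the reported proportion (illustration only)**

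The documents give neither a true reaction rate nor a capture rate, so both are assumed. Let n = 23, p = true per-patient reaction rate, and r = probability that a reaction is captured per chance. The recorded rate is:

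- (a) one capture chance per patient: p × r
- (b) reactions independent across injections, each week-1 check capturing independently: 1 − (1 − q·r)³, with q = 1 − (1 − p)^(1/3)
- (c) a reacting patient reacts at all three injections, each check capturing independently: p × [1 − (1 − r)³]

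For p = 50%, q = 20.6%. The exact (Clopper-Pearson) interval is 10.2% to 48.4% for 6/23 and 13.2% to 52.9% for 7/23, so it lies wholly below 50% when 6 or fewer patients are recorded. The probability of that is:

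| Case, p = 50% | r = 25% | r = 50% | r = 80% |
|---|---|---|---|
| (a) | 98% | 65% | 12% |
| (b) | 96% | 53% | 9% |
| (c) | 49% | 6% | 2% |

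With full capture it is 1.7%. At p = 30% the same cases give 75/31/6%, 71/27/5% and 21/4/2%.

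These figures give injection-day checks no credit. Add one injection-day chance with an assumed 50% capture, so that capture per chance becomes 1 − (1 − r)(1 − 0.5) = 62.5%, 75% and 90%. At p = 50% the results fall to:

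| Case, p = 50%, injection-day check credited | r = 25% | r = 50% | r = 80% |
|---|---|---|---|
| (a) | 39% | 18% | 5% |
| (b) | 29% | 13% | 4% |
| (c) | 3% | 2% | 2% |

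**The case against.** The strongest reply is that Section 8.2 already does most of the work. It requires specific questioning at each contact and examination where appropriate. It also asks that events be written down at once and that every adverse event in the study period be recorded. Staff are present during the injections and can record what they see. A patient asked on day 7 can usually say whether the scalp hurt or reddened a few days before, and Section 7.2 needs only yes or no. For occurrence, this largely stands. It does not restore examiner-observed signs that have resolved, or a pain level, and Section 3.4 names both.

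Other parts of the reply also stand. Section 6 item d does not claim to be exhaustive. The Baseline column carries no adverse-event mark in either arm, so the omission in Arm A may be an editing convention. The safety hypothesis in Section 7.2 concerns significant complications, on which brief redness has little bearing. The protocol text names no pain scale, grading or recall period, but the case report form, questionnaire, adverse-event worksheet and separate monitoring plan were not available and may contain them.

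Three stronger readings are tempting, and the documents do not support them:

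- *That local reactions are expected.* Section 1.4 calls them possible and gives 2-3 days as an upper limit.
- *That the comparison with minoxidil must favour PRP.* Missed brief reactions push that way, but 6 scheduled contacts against 1 push the other way. The net direction cannot be determined.
- *That McNemar's test should be confined to end-of-period visits.* Section 7.2 plans to compare occurrence. A 12-week recall question, asked four weeks after the last injection, would miss most brief PRP reactions. Unequal ascertainment in that test is a separate issue.

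**Conclusion.** The point holds as an optional refinement. The timing facts are certain: six of six dedicated site assessments on day 7, no scheduled contact on days 1-3, and no section placing a check after the injection. The likely consequence is a partial loss, mainly of brief visible signs and of pain level or grade, with less effect on yes/no occurrence. Later or lasting reactions can still be found at week 1 and at months 3, 5, 8 and 12.

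The size is unknown. The calculated range rests wholly on assumed reaction and capture rates, and at a true rate of 50% it runs from about 2% (close to the 1.7% under full capture) to 98%. A reader might take the upper figures as a finding of serious bias. They require low capture under direct questioning and no capture at all on the injection day, and no section supports either.

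**What to change.** Keep the week-1 check, and make these changes:

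1. Reconcile Section 6 item d, the Section 6.1 calendars and Section 8.2 by marking the adverse-event check as post-injection at all six injection visits, including Arm A Baseline.
2. At that check record a 0-10 pain score, a swelling/erythema/warmth checklist graded none, mild, moderate or severe, and whether topical anaesthetic was used (Section 5.4 leaves its use to discretion).
3. At week 1 add one fixed recall question: worst pain 0-10, any swelling, redness or warmth since the injection, and how many days it lasted.
4. Report these added items as descriptive PRP tolerability: proportions with exact 95% confidence intervals, worst grade and duration, with pain as a separate score distribution. Keep them out of the McNemar test. Six discordant pairs all in one direction give an exact two-sided p = 2 × 0.5⁶ = 0.031, so 6 of 23 patients (26%) with an event found only by the extra PRP checks, and none the other way, would reach the 0.05 threshold.
5. State in the report that adverse events are sought more intensively on PRP than on minoxidil: 6 versus 1 scheduled contacts now, 7 versus 1 once a post-injection check at the first injection is counted.

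The cost is one short form, with about 69 post-injection entries and 69 recall answers (23 × 3 each), and no extra visits. The reported PRP reaction rate may look less favourable. If the forms that were not available already contain these items, only changes 1, 4 and 5 remain.
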